Project title: A Comparison of the Post-Cesarean Section Analgesic Effects of Neuraxial Duramorph vs. Bilateral Transversus Abdominal Plane (TAP) Block With Combined Bupivacaine and Liposomal Bupivacaine (Exparel).

Clinicaltrials.gov name

A Comparison of the Post-C/S Analgesic Effects of Neuraxial Duramorph vs Bilateral TAP Block With Liposomal Bupivacaine

Submitted to IRB 4-5-2018

IRB# 2018-4-1-MMC

NCT: 03638011

Summary/Program Objective:

The primary objective is to reduce or eliminate the use of all narcotics/opiates for post Cesarean section pain management. We hypothesize that in comparison with epidural or intrathecal Duramorph, a TAP block with liposomal bupivacaine (Exparel) will provide better, longer-acting pain control and will significantly reduce the use of post-operative IV or p.o. opiates. This is a prospective, randomized clinical trial. We will compare the analgesic efficacy and duration of an ultrasound guided bilateral TAP Block (with combined bupivacaine and liposomal bupivacaine) to Duramorph (an opiate). Neuraxial duramorph provides approximately 24 hours of pain relief (analgesia), whereas a bilateral TAP block with liposomal bupivacaine is expected to provide up to 72 hours of analgesia. The patient's analgesia will be assessed by reviewing patient-reported pain intensity based on an 11-point numeric rating scale (NRS; 0= no pain, 10= worst possible pain) and post-operative opiate usage. Secondary objectives include a comparison of the opiate related post-surgical adverse events (AEs) (defined as somnolence, sedation, confusion, respiratory depression, dry mouth, nausea, vomiting, constipation, urinary retention and pruritus), and overall satisfaction with their postsurgical analgesia (patient-reported, using an 11 point scale whereby 0= not at all satisfied and 10= extremely satisfied) at hospital discharge.

Purpose of the study:

To determine if a bilateral transversus abdominal plane block with combined bupivacaine and liposomal bupivacaine can provide safe, effective, long-acting pain control that minimizes narcotic usage.

1. Specific Aims:

All patients will have neuraxial anesthesia (either a spinal or epidural) for their non-urgent or elective Cesarean section.

The control group (Group 1) will receive either intrathecal or epidural Duramorph (preservative-free morphine sulfate). Post-operatively, participants will have orders to receive, on an as-needed basis, IV/oral acetaminophen and/or IV/oral non-steroidal anti-inflammatory drugs (NSAIDS) for mild-moderate pain, and narcotics for severe pain; specifically- oxycodone or hydromorphone. All patients must receive acetaminophen and NSAIDS (unless contraindicated) before receiving narcotics. This multi-modal pain management regimen is our current standard of care.

The experimental group (Group 2) will also receive a spinal or epidural anesthetic. This group will not receive neuraxial Duramorph for post-operative pain. Instead, the patient will receive an ultrasound guided bilateral TAP block with a combination of bupivacaine and liposomal bupivacaine solution immediately after the Cesarean section. Additionally, they will receive the same post-operative analgesia orders as group 1.

Specific Aim 1) To show that participants in the TAP block group will have better and longer acting pain relief than the Duramorph group. We will record and compare patient-reported post-operative pain intensity using an analogue visual score card with an 11-point numeric rating scale at 6, 24,48 and 72 hours.

Specific Aim 2) To show that the TAP block group will use less post-operative narcotics than the Duramorph group. We will measure and analyze the times at which participants in both groups request narcotics and the amount administered. We will also record each participant's pain level prior to receiving narcotics. It is anticipated that participants in TAP Block group will need significantly less post-operative narcotics when compared to the Duramorph group (standard of care)

Specific Aim 3) The TAP block group will have a decreased incidence of opiate- related side effects such as somnolence, sedation, confusion, respiratory depression, dry mouth, nausea, vomiting, constipation, urinary retention, and pruritus (itching).

Specific Aim 4) To measure patients' overall satisfaction with their postsurgical analgesia. Using an 11 point scale where 0= not at all satisfied and 10= extremely satisfied, we will record their overall satisfaction with their postsurgical analgesia. It is anticipated that participants in the TAP block group would report their pain control as being better than participants in the Duramorph group.

Analysis of our initial data, presented below, anticipates that group 2 will have better post-operative analgesia with a longer duration and less post-operative narcotic usage and fewer opiate-related adverse effects.

2. **Background / Significance:**

Postsurgical pain is a significant concern for patients undergoing surgical procedures. Many patients are concerned about pain. In a recent survey, (1) nearly 80 percent of patients had some anxiety over post-operative pain, with almost 2/3 of those concerned with pain reporting moderate to severe post-operative pain. Although, narcotics play a significant role in providing post-operative pain relief, they often cause nausea, vomiting, constipation, pruritus. More worrisome is the opiate related life threatening risks of hypoventilation and respiratory failure. Additionally, there is the public health concern of unused and unmonitored prescription opiates being used for nonmedical purposes that could cause injuries or even deaths (2).

Liposomal Bupivacaine suspension is currently indicated for single-dose infiltration into the surgical site for postsurgical analgesia. This formulation combines bupivacaine with DepoFoam®, a proven product delivery technology that delivers medication over an extended time period. A single dose of Liposomal Bupivacaine is shown to provide significant reductions in cumulative pain scores with a decrease in opioid consumption.

Exparel® was FDA approved in 2011.

We have used Exparel® infiltrated bilaterally into the TAP to provide prolonged postoperative analgesia in patients undergoing umbilical hernia repairs. TAP blocks have been successfully used for post-operative pain relief for surgical procedures involving incisions of the mid and lower abdominal wall (3,4). Our experience has demonstrated that a TAP block with non-liposomal bupivacaine provides 12-18 hours of analgesia, whereas, TAP blocks utilizing the extended release liposomal bupivacaine provide up to 72 hours of pain relief (5,6).

Exparel and Cesarean sections

TAP Blocks have been used to reduce post-cesarean section opiate administration and pain scores. Previous studies with either bupivacaine or ropivacaine alone have demonstrated a reduction in rest pain at 6, 12, and 24 hours--but not at 48 hours.

We just completed another small case series that showed the prolonged analgesic effects of liposomal bupivacaine in bilateral TAP blocks in a cohort of patients who have undergone cesarean section with neuraxial anesthesia. (6).

After IRB approval, this Center conducted a trial of Exparel. We performed a bilateral TAP block using the combination of bupivacaine and liposomal bupivacaine in twelve patients who were scheduled for elective C-Section under neuraxial anesthesia. These patients also received neuraxial preservative free morphine for postoperative analgesia. An ultrasound guided bilateral

TAP block was performed at the end of the surgery.. 20ml of liposomal bupivacaine mixture (20 ml of liposomal bupivacaine mixed with 20 mls 0.25% bupivacaine) was injected on each side (a total of 20 ml was injected into each side.) The patients were ordered acetaminophen and ketorolac for mild/moderate pain and oxycodone for severe/breakthrough pain. Patient postoperative analgesia VAS scores and administration of opiates were recorded after 6, 12, 24, 48, and 72 hours.. Patients who received bilateral TAP blocks with liposomal bupivacaine had pain scores (on a scale of 0-10) of 1.0 ± 1.4 , 1.4 ± 2.1 , 1.7 ± 1.9 , 1.9 ± 3.3 and 1.9 ± 2.3 (mean \pm SD) at 6, 12, 24, 48 and 72 hours respectively (Table 1). At 48 hours, long after the Duramorph had worn off, patients had an average pain score 1.9 suggesting that they had excellent analgesia from the TAP block alone.

Overall, patients who received the bilateral TAP blocks used little narcotics. On postoperative day 3 (72 hour after the TAP block), only one patient requested and received 5 mg of oxycodone 3 times.. Within 24 hours, 2 patients used acetaminophen/oxycodone. One of these 2 patients received acetaminophen/oxycodone for anticipated pain in a monitored unit despite having only pain scores of 0.

On an 11 point scale, the mean patient satisfaction score was 9.3 ± 1.1 (Table 2).

Table 1: Patients pain scores after bilateral TAP Block after cesarean section

Table 1							
	6	12	24	48	72	Overall	
	hours	hours	hours	hours	hours	l	
Pain score	1.0	1.4	1.7	1.9	1.9	1.5	Mean
	1.4	2.1	1.9	3.3	2.3	2.2	SD

Patient pain scores from all 12 patients were recorded at every visit. They were asked on a scale of 0-10, where 0 was no pain and 10 was the worst pain you can imagine: how do you rate your pain?

Table 2: Patient satisfaction with their pain management

Table 2

	6 hours	12 hours	24 hours	48 hours	72 hours	Overall 1	
score	9.33	9.08	9.33	9.33	9.22	9.26	Mean
	1.07	1.24	1.15	0.78	1.30	1.07	SD

Patient satisfaction were recorded from all 12 patients at either last visit or they were called at home. There were asked on a scale of 0-10, where 0 was the worst and 10 was the best, how do you rate your pain management?

The mean pain score in the TAP block group when first requesting pain medication was 1.3 ± 2.3 on a scale of 0-10. The mean pain score at all request for pain medication was 0.8 ± 1.8 . These results demonstrate that the patients receiving the TAP blocks with liposomal bupivacaine had profound postoperative pain relief (Table 1) and used minimal postoperative narcotic.

These results were better than expected. For comparison purposes, we performed a chart review. We selected a similar cohort of the first 60 subjects for a chart review, beginning on January 1, 2012, who underwent elective Cesarean delivery with a spinal anesthetic consisting of hyperbaric 0.75% bupivacaine, fentanyl 15mcg, and 0.3mg Duramorph™ without TAP blocks. Thirty-nine out of 60 patients in this group received Percocet postoperatively. Pain scores were recorded only at the time when the patient was requesting pain medication. The mean pain score at the first request for pain medication was 5.3 ± 1.8 . The mean pain score recorded at all requests for pain medication was 5.5 ± 1.9 . Patient in this group used an average 24 ± 17 mg of oxycodone. Compared to the chart review (neuraxial Duramorph), the number of patients using narcotics in the liposomal bupivacaine TAP blocks group was less than the chart review group (which is our standard of care group): 3/12 vs 39/60 $p < 0.013$, respectively. Within 24 hours, the difference in the use of narcotic between the two groups was not significant (< 0.629); however, after 48 hours the TAP block group used significantly less narcotic (< 0.02) than the control group (2/12 for the TAP Block group vs. 32/60 Duramorph (chart review) group). On postoperative day 3, an additional patient in the TAP block group requested and received 5 mg of oxycodone 3 times. (The liposomal bupivacaine TAP block group used significantly less opioids, 1 out of 12, on day 3 compared to the Duramorph group, (22 out of 60, $p < 0.05$).

The combination of these results suggest that the patients receiving TAP blocks with liposomal bupivacaine had significant postoperative pain relief (Table 1) and used little postoperative narcotic in comparison with neuraxial Duramorph.

Since our initial study of TAP blocks, (5), we have improved and refined our administration technique. We now consider liposomal bupivacaine to be like an infusion that should be initiated with a bolus (a large initial dose) in order to achieve therapeutic levels that will be maintained by liposomal bupivacaine. As per the Exparel liposomal bupivacaine package insert, bupivacaine HCl and EXPAREL may be administered simultaneously in the same syringe, and bupivacaine HCl may be injected immediately before EXPAREL as long as the ratio of the milligram dose of bupivacaine HCl solution to EXPAREL does not exceed 1:2' (7). Exparel® can be given with ½ the total dose of the bupivacaine found in the liposomes (266mg). That means we can co-administer 133 ml of 0.25% bupivacaine (=53.2 ml of 0.25% bupivacaine) with the liposomal bupivacaine. We will be adding 40 ml of the 0.25% bupivacaine, which is well below the maximal dose. From our experience and personal communications from other anesthesiologists, administering 30-35 ml on each side of the TAP block results in the 'best' block. We will explain our TAP block in the Methods section.

3. Research Design and Methods:

This is specifically for postpartum women. The purpose of this study is to test the effectiveness of Exparel (liposomal bupivacaine) administered in a bilateral TAP block to provide better analgesia after Cesarean section than neuraxial duramorph, which is the current standard of care: neuraxial Duramorph, and minimize use of post-operative narcotics and their annoying common side effects at one of the most enjoyable moments of life: having a new baby.

This is a prospective, randomized study evaluating the effectiveness of abdominal analgesia when using 266 mg EXPAREL delivered into the bilateral TAP blocks. TAP blocks are an excellent method for providing adequate analgesia following lower abdominal surgery (3-6). To be eligible for the study, the patient has to be undergoing a non-urgent Cesarean section (either elective, or for non-urgent conditions such as failure to progress) with neuraxial anesthesia via an epidural, spinal or combination epidural/spinal. When patients arrive for their Cesarean section they will be assessed if they are eligible for the study and they will be asked to participate in the study after the risks and benefits are explained. If a patient does not want to participate, they will be offered TAP blocks with regular bupivacaine. Those patients who wish to participate will be asked to sign a study consent form. Patients that decide to participate in this study will be randomized to either group 1 or group 2 (like the

flip of a coin). Both groups will receive standard neuraxial anesthesia for their Cesarean Section and post-operative standard of care breakthrough medications for post-operative pain control. They will be randomized to receive either (group 1) standard neuraxial anesthesia with neuraxial Duramorph for post-operative pain or (group 2) standard neuraxial anesthesia without neuraxial Duramorph and a transversus abdominal plane (TAP) blocks immediately after surgery, with a mixture of bupivacaine and Exparel, for post-operative analgesia.

There are only two groups in this study: Group 1 will have our present standard of care: neuraxial anesthesia, with Duramorph added to the epidural or spinal for post-operative pain. Group 2 will also have neuraxial anesthesia but will receive bilateral TAP blocks for post-operative pain control with 40 ml of 0.25% regular standard bupivacaine and with 20 ml of liposomal bupivacaine (Exparel) and 10-20 ml of normal saline (a salt solution, for a total of 70-80mls: 35-40 ml on each side). The TAP block plane will be identified with ultrasound. A 100 mm needle will be ultrasound guided into the TAP plane. 5-10 milliliters of normal saline will be used to hydro-dissect the plane. After hydro dissection 15 ml of 0.25% regular standard bupivacaine will be injected followed by 10 milliliters of liposomal bupivacaine (Exparel) diluted with 5 ml of 0.25% regular standard bupivacaine. This will be repeated on the opposite side. We will follow pain levels closely after the Cesarean section. If patients request medication for breakthrough pain, they will be given Tylenol, first. If the pain persists, they will be given Toradol 30 mgs, unless contraindicated. For persistent pain, they may receive another dose of 30 mgs of Toradol, but for severe pain they will be offered oxycodone 5-10 mg, depending on the intensity of the pain. Patients must be given both Tylenol and Toradol, unless contraindicated, before receiving narcotics for severe pain. We will ask you a set of questions to assess to quality of analgesia (pain control): 1) How is your pain at that time point? 2) What was your highest pain score? And 3) Did you require narcotic pain medication, when did you receive it and what was your pain level at that time? To assist your evaluation of your pain, we will show you a card that has a visual analogue (Faces) pains scale combined with numerical (0-10) analogue scale (0 is no pain, 10 is the worst pain you can imagine). We will be recording your pain at

- 6 hours after the end of anesthesia or the TAP block
- 24 hours after the end of anesthesia or the TAP block.
- 48 hours after the end of anesthesia or the TAP block.
- And at 72 hours after the end of anesthesia or the TAP block.
- Before you leave the hospital, we will ask you to rate your pain control.

At all-time points patients and/or nurses taking care of the patient will be asked about: somnolence (sedation or excessive tiredness), respiratory depression, hypoxia, dry mouth, nausea, vomiting, itching, constipation, urinary retention, sedation, and confusion.

We will also record time and date of any and all post-operative narcotics used by the patient as well as their pain scores just prior to receiving narcotics.

Additionally, patients will be asked about their overall satisfaction with postsurgical analgesia at the end of their hospital stay. If after Day 10±5, the investigator is made aware of an AE that occurred during this period of time, this will be reported to the IRB.

Eligibility Criteria:

Inclusion Criteria:

- Females, aged 18-45 years inclusive and ASA physical status 1-3.
- Undergoing non-urgent Cesarean section with neuraxial anesthesia/analgesia.
- Subjects must be physically and mentally able to participate in the study and complete all study assessments.
- Subjects must be able to give fully informed consent to participate in this study after demonstrating a good understanding of the risks and benefits of the proposed components of the TAP infiltration.

Exclusion Criteria:

- History of hypersensitivity or idiosyncratic reactions to amide-type local anesthetics
- Any subject whose anatomy, or surgical procedure, in the opinion of the Investigator, might preclude the potential successful performance of a bilateral TAP infiltration.
- Any subject who in the opinion of the Investigator, might be harmed or be a poor candidate for participation in the study.
- Any subject, who in the opinion of the Investigator, is on chronic pain medicine, including large doses of NSAIDs.
- Subjects who have received any investigational drug within 30 days prior to study drug administration, or planned administration of another investigational product or procedure during their participation in this study.

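### Do unlabelled one-sided p-values in the pilot comparison, and an unstated test side and 72 h contact route, call for a change to the plan?

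*Combined protocol and SAP*

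**What the plan says.** The pilot compares 12 TAP block patients with a chart review of 60 patients who had neuraxial Duramorph (section 2, Background / Significance). Opioid users are 3/12 vs 39/60 overall (p < 0.013) and 2/12 vs 32/60 in the 48-hour comparison (< 0.02). For day 3, the TAP group "used significantly less opioids, 1 out of 12, on day 3 compared to the Duramorph group, (22 out of 60", with p < 0.05. For the first day it says "Within 24 hours, the difference in the use of narcotic between the two groups was not significant (< 0.629", with no control count. No test or side is named for any of the four.

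On completeness, the pilot methods say pain scores and "administration of opiates were recorded after 6, 12, 24, 48, and 72 hours". The Table 1 note says "Patient pain scores from all 12 patients were recorded at every visit". The Table 2 note says "Patient satisfaction were recorded from all 12 patients at either last visit or they were called at home".

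The Specific Aims section uses these data as rationale: "Analysis of our initial data, presented below, anticipates that group 2 will have better post-operative analgesia with a longer duration". For the trial, Aim 2 says "We will measure and analyze the times at which participants in both groups request narcotics and the amount administered". Section 3 (Research Design and Methods) schedules assessments at 6, 24, 48 and 72 hours. Its question set asks whether narcotics were needed, when, and at what pain level. It does not describe contact after discharge. The supplied text gives no alpha and no test side.

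**The concern.** Three things catch the eye.

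- The printed pilot p-values look like one-sided results presented without a label. A reader who assumes the usual two-sided convention would take the day-3 difference as established at 5% when it is not. Day 3 is the latest period compared, so it bears on the expected longer duration.
- The 72-hour satisfaction mean in Table 2 does not fit 12 whole-number scores, which suggests some patients were not reached at that time.
- The trial relies on 72-hour data but does not say how they are obtained from a patient who has gone home. If day 3 were seen more often in one arm than in the other, a comparison of opioid use could be distorted. With no stated side, a borderline result could be read either way.

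**Working it through.** **Day 3, reproducing the printed claim.** Inputs are 1/12 and 22/60 (section 2), so 23 users among 72 patients. Under Fisher's test the number of TAP users X is hypergeometric: P(X = k) = C(23,k)·C(49,12−k)/C(72,12).

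- P(0) = 0.00601 and P(1) = 0.04362, so the one-sided p is 0.0496. This agrees with the printed p < 0.05.
- The two-sided test adds the upper-tail outcomes no more likely than the one observed: P(7) = 0.03043, P(8) = 0.00676, P(9) = 0.00098, P(10) = 0.00009, total 0.0383. The two-sided p is 0.0496 + 0.0383 = 0.088.

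**The three comparisons with printed counts.**

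| Comparison | Printed | Fisher one-sided | Fisher two-sided | Pearson | Yates | Likelihood ratio |
|---|---|---|---|---|---|---|
| Any use, 3/12 vs 39/60 | < 0.013 | 0.0125 | 0.022 | 0.010 | 0.025 | 0.010 |
| 48 h, 2/12 vs 32/60 | < 0.02 | 0.0201 | 0.027 | 0.0202 | 0.045 | 0.015 |
| Day 3, 1/12 vs 22/60 | < 0.05 | 0.0496 | 0.088 | 0.055 | 0.114 | 0.035 |

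One-sided Fisher is the only column that fits all three once rounding is allowed; the literal < 0.02 is just missed. Pearson fits the 48-hour value equally well, so that row does not discriminate.

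**The 24-hour value.** The TAP count is 2 of 12 (section 2). A search over control counts from 0 to 60 finds 0.629 only for one-sided Fisher at 11/60 (0.6287). That count is not printed, so the fourth match is an inference.

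**Table 2 at 72 hours (mean 9.22, SD 1.30).** With 12 whole-number scores the nearest means are 110/12 = 9.17 and 111/12 = 9.25. For n of 12 or fewer only 83/9 = 9.22 fits. The SD is attainable there: scores of 6, three 9s and five 10s sum to 83 with SD 1.302. The overall mean agrees too: (112 + 109 + 112 + 112 + 83)/57 = 528/57 = 9.26. The overall SD would be 1.078 against a printed 1.07, so nine patients is likely but not proven. This concerns satisfaction only. Table 1 at 72 hours (1.9, SD 2.3) fits 12 patients.

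**How far day 3 could move an any-use comparison.** Read the counts as cumulative: control 32/60 = 53.3% by 48 hours and 39/60 = 65.0% overall; TAP 2/12 = 16.7% and 3/12 = 25.0%.

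- Day 3 seen in both groups: 65.0 − 25.0 = 40.0 points (two-sided p = 0.022).
- Day 3 unseen in every control: 53.3 − 25.0 = 28.3 points (0.113).
- Day 3 unseen in every TAP patient: 65.0 − 16.7 = 48.3 points (0.003).

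The last two are extremes. The documents give no length of stay and no sign of unequal follow-up between the trial arms.

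**The case for a change.** The best case for a change is that the correction is cheap and the defect real. The word significantly, applied to day 3, rests on a side the text does not disclose, and these data are offered as grounds for expecting longer-lasting analgesia. The trial then repeats the silence: no side, no alpha, and no route to a patient at home, although the pilot used telephone calls. A few sentences would settle all of it.

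The factual part stands. The pilot p-values should have been labelled, and the day-3 result does not reach 5% two-sided by Fisher. What does not stand is the step from there to a fault in the plan.

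- Longer duration does not rest on day 3 alone. Section 2 also argues it from mean pain scores of 1.9 at 48 and at 72 hours. It words the 2/12 vs 32/60 comparison as after 48 hours; read literally, that comparison survives two-sided at 0.027. The reference to "an additional patient in the TAP block group requested and received 5 mg of oxycodone 3 times" favours a cumulative reading instead, but both readings are open.
- The Table 2 note says all 12 gave a rating at a last visit or by telephone. It does not say all 12 did so at every time point; only the Table 1 note says that. Nine ratings at 72 hours can be squared with it.
- The 28.3 and 48.3 point figures require the loss of day 3 in one whole group of a non-randomised comparison. They also concern any use, whereas Aim 2 names request times and amounts.
- Discharge governs the satisfaction rating and Day 10±5 governs adverse event reporting. Neither is shown to compete with 72 hours as the end of the opioid record, and nothing suggests that unseen use would be counted as zero.

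**Conclusion.** No change to the plan follows. The pilot paragraph has a labelling slip: two-sided Fisher gives 0.022, 0.027 and 0.088 in place of the printed < 0.013, < 0.02 and < 0.05, and only day 3 crosses 0.05. The observed direction is unaffected (8.3% vs 36.7%). A comparison of 12 treated patients with a chart review, in which the TAP patients also received neuraxial morphine, is weak support for this trial on either side of the test. The supplied text derives no sample size, threshold or analysis from it.

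The missing test side, alpha and 72-hour contact route are unstated details. A competent analyst would use a two-sided 5% test, treat unobserved opioid use as missing, and report the numbers observed by arm. Staff committed to a 72-hour assessment would telephone a patient who had left, as the pilot staff did for satisfaction.

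This rests on three assumptions: that the background p-values are not carried into the trial's own inference, that 72-hour follow-up is sought in the same way in both arms, and that the 24-hour control count of 11/60 remains an inference that nothing depends on.

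### Does coin-flip allocation, with no blocks and no strata for neuraxial technique, weaken the comparison of Duramorph with TAP block?

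*Combined protocol and SAP*

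**What the plan says.** Section 3 (Research Design and Methods) describes allocation in one sentence, which runs across a page break: "Patients that decide to participate in this study will be randomized to either group 1 or group 2 (like the" and then "flip of a coin). Both groups will receive standard neuraxial anesthesia for their Cesarean Section". No block size, stratification factor, sequence generation or concealment is given anywhere in the supplied text.

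The design has two arms: "There are only two groups in this study". Section 1 (Specific Aims) gives the anaesthetic as "All patients will have neuraxial anesthesia (either a spinal or epidural) for their non-urgent or elective Cesarean section", while section 3 admits women "with neuraxial anesthesia via an epidural, spinal or combination epidural/spinal".

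The control drug follows the technique. Section 1 says "The control group (Group 1) will receive either intrathecal or epidural Duramorph (preservative-free morphine sulfate"), and section 3 repeats it: "with Duramorph added to the epidural or spinal for post-operative pain". The Group 2 TAP block is described once, with no variation by technique.

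The supplied text states no sample size, significance level, power or analysis model.

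**The concern.** Three features together suggest a missed opportunity. First, independent coin flips let arm sizes drift apart in a small trial. Second, they let the share of epidural anaesthesia differ between arms by chance. Third, technique is more than background here, because in Group 1 it decides whether morphine is given intrathecally or epidurally. If the route affects pain relief, technique is the obvious stratification factor, and leaving it out puts its variation into the error term. The combined technique appears in one section and not in the other, so its stratum would also be undefined.

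At stake would be some power on pain scores and opioid use, lost for want of a slightly more elaborate randomisation list.

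**Working it through.** **Validity.** Under a fair coin, assignment is independent of technique, so chance imbalance adds variance but no bias. Check by simulation: N = 60, 30% epidural, 1-point technique effect, SD 2.2, no treatment effect, 40,000 trials. The mean error of the unadjusted difference was 0.003 points (Monte Carlo SE 0.003). Its variance was 0.342, against 2.2² × 4/60 = 0.323 when balanced, about 6% more. In a separate simulation with the technique effect in both arms, type I error under the unadjusted coin flip was 4.9-5.0%.

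**Target.** Section 1 calls the control regimen the current standard of care and allows either route within it. The average effect over the enrolled mix is therefore a coherent quantity, and it does not require equal mixes by design.

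**Inputs for precision.** SD 2.2 is the overall value in Table 1 of section 2, from 12 women who had both TAP block and neuraxial morphine; it is a rough stand-in for either trial arm. Everything else is assumed: N = 40, 60 or 100; 30% epidural; technique effect 1 point; two-sided 5%; true differences 2.00, 1.62 and 1.25 points, which give 80% power with equal arms.

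**Size of the chance imbalance.**
- Arm size, Binomial(N, 0.5), 95% range: 14-26 of 40, 22-38 of 60, 40-60 of 100.
- Average variance inflation, E[(1/n1 + 1/n2)/(4/N)]: 2.7%, 1.8% and 1.0%. By the normal approximation, power falls from 80% to 79.0%, 79.3% and 79.6%.
- Exact probability that the epidural share differs between arms by 15 points or more (12, 18 and 30 epidural women): 0.319, 0.216, 0.105.
- Variance explained by technique if it acts in both arms: 0.30 × 0.70 × 1² / (0.21 + 2.2²) = 0.21/5.05 = 4.2%.

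**Does stratification help?** Power in %, 30,000 trials per setting, blocks of 2 and 4; simulation error of a difference about ±0.6 points.

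| Technique effect | N | Coin, unadjusted | Plain blocks, unadjusted | Stratified blocks + covariate | Stratified minus plain blocks |
|---|---|---|---|---|---|
| Group 1 only | 40 | 78.1 | 79.4 | 79.5 | +0.1 |
| Group 1 only | 60 | 78.5 | 79.6 | 79.3 | -0.3 |
| Group 1 only | 100 | 79.0 | 79.2 | 79.6 | +0.4 |
| Both arms | 40 | 77.1 | 78.4 | 80.1 | +1.7 |
| Both arms | 60 | 77.4 | 78.3 | 80.0 | +1.7 |
| Both arms | 100 | 78.1 | 78.2 | 79.7 | +1.5 |

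The reason for suspecting technique is the Duramorph route, which is the Group 1 scenario. There, stratifying and adjusting adds nothing detectable to plain blocking. A separate run of 8,000 trials per setting (error about ±1.2 points) agrees: 78.7, 79.0 and 79.5% with strata and covariate, against 79.2, 78.5 and 79.7% with plain blocks, differences of -0.5, +0.5 and -0.2. The gain over a coin flip in the both-arms rows (3.0, 2.6 and 1.6 points) needs technique to affect pain even in women who receive no neuraxial morphine. The documents give no evidence of that.

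**Price of small blocks.** Group 2 receives an additional, visible procedure, and the supplied text describes no blinding, so past allocations could be known to staff. Always guessing the arm that is behind gives, on average, 1.5 correct of 2 in a block of 2 and 2.83 of 4 in a block of 4. With both sizes equally likely, (1.5 + 2.83)/6 = 72%, against 50% under a coin. The simulated power gains use exactly these block sizes.

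**The case for a change.** The strongest reply is that the remedy is nearly free: two lists instead of one, a recorded technique, one degree of freedom and no extra patients. Feasibility is plausible, since "When patients arrive for their Cesarean section they will be assessed if they are eligible for the study". The loss could also exceed the figures above. With a 2-point technique effect in both arms and no adjustment, power would fall from 80% to 75.0% at 20% epidural or 72.3% at 50%. Nor can the historical controls show that technique is unimportant, because the chart review in section 2 covered spinal anaesthesia only.

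Part of this stands. A stratified list is a respectable choice, and a large technique effect in both arms would make it worthwhile. But that effect is an assumption with nothing in the documents behind it, and the power figures concern pain scores, while the stated primary objective is to reduce or eliminate opioid use. The text does not say that technique is fixed before allocation, which stratification would require. Nor is the change free once predictability in an apparently unblinded trial is counted.

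The differing lists of techniques in sections 1 and 3 would matter for defining strata. They do not affect the validity of an unstratified comparison.

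**Conclusion.** The concern does not hold. Followed as written, coin-flip allocation gives a valid comparison of the two regimens over the techniques enrolled. The average power cost of unequal arm sizes is about 0.4 to 1.0 points for 100 down to 40 women. Stratification by technique shows no gain beyond plain blocking if technique acts through the Duramorph route. It gains about 1.5 to 1.7 points over plain blocking only if a 1-point effect in both arms is assumed. Against this stands a guess rate of about 72% with the small blocks that were simulated. Experienced statisticians would differ on that exchange, so keeping simple randomisation is a defensible choice.

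The conclusion rests on assumed values for sample size, technique mix, technique effect and target difference, on an SD from 12 pilot women, and on assignment that is truly random and concealed. The supplied text does not describe sequence generation or concealment, and the coin-flip phrase may be lay wording for a 1:1 ratio, since nearby text addresses the participant directly. That is missing detail about the method, separate from the question of blocks and strata.
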